13.1.6 Continuous Physical Measures

- a) Height (cm)
- b) Weight (kg)
- c) BMI
- d) Bone mineral density (DEXA) z score
- e) Blood pressure; systolic, diastolic, mean
- f) Safety bloods

13.1.7 Binary Physical Outcomes

- a) Adverse events
- b) Puberty staging (Tanner staging, both clinical and self-reported)

13.2 HORIZON INTENSIVE

13.2.1 Primary Outcome

1. The primary outcome for PATHWAYS HORIZON INTENSIVE is the quality of life of children referred to national gender services for young people in the UK, measured using the CYP self-report version of the KIDSCREEN-10 questionnaire.

13.2.2 Scales of Gender-Related Distress, Mental Health Symptoms and Physical Health measures:

- a. Utrecht Gender Dysphoria Scale – Gender Spectrum (UGDS-GS)
- b. Revised Children's Anxiety and Depression Scale (RCADS)
- c. Body Image Scale – Gender Spectrum (BIS-GS)
- d. Parental Attitudes of Gender Expansiveness Scale for Youth (PAGES-Y)
- e. SCOFF questionnaire
- f. Sexual attraction questionnaire
- g. ALSPAC measure
- h. Gender identity question
- i. Adolescent Primary Care Traumatic Stress Screen (APCTSS)
- j. KIDSCREEN-52
- k. Height (cm) and weight (kg)
- l. Physical health diagnoses

13.2.3 Rates of Suicidal Ideation, Non-Suicidal Self-Injury, Hospitalizations, Mood Symptoms, Behavioural and Functional Difficulties:

- a. Ask Suicide-screening Questions (ASQ)
- b. Child Behaviour Checklist (CBCL)
- c. Youth Self-Report (YSR)
- d. Difficulties in Emotion Regulation Scale – 18 (DERS-18 for CYP; DERS-29 for parents/caregivers)
- e. Hospitalisations of participants

13.2.4 Experiences of Therapeutic Options:

- a. Rates of referral to, uptake of, and completion of psychological therapy, occupational therapy, speech and language therapy, clinical nursing, youth work support, school/college support, and non-endocrine pharmacological treatments.

13.2.5 Cognitive Assessments:

- a. Wechsler Intelligence Scale for Children (WISC-V)
- b. Delis-Kaplan Executive Function System (D-KEFS)
- c. Child and Adolescent Memory Profile (CHAMP)
- d. Memory Validity Profile (MVP)
- e. Behaviour Rating Inventory of Executive Function (BRIEF)

13.2.6 Continuous Physical Measures:

- a. Height (cm)
- b. Weight (kg)
- c. BMI
- d. Bone mineral density (DEXA) z score
- e. Blood pressure; systolic, diastolic, mean
- f. Safety bloods

13.2.7 Binary Physical Outcomes:

- a. Adverse events
- b. Puberty staging (self-reported)

The electronic version of this document is the latest version. It is responsibility of the individual to ensure that any paper material is the current version. Printed material is uncontrolled documentation.

13.3 CONNECT

- a. Brain Structure: Longitudinal trajectories of brain tissue volume (especially in the basal ganglia, pituitary gland and hypothalamus) using standard weighted T1 and T2 images.
- b. Brain Structure: Longitudinal trajectories of microstructure in cortical white matter using diffusion MRI and T2* images.
- c. Brain Metabolites: Longitudinal changes in brain metabolites in the globus pallidus and putamen (basal ganglia) using magnetic resonance spectroscopy.
- d. Brain function: Functional connectivity between the basal ganglia (and other subcortical structures) with cortex using functional MRI.

These outcomes are exploratory and there is no defined primary outcome.

Longitudinal brain trajectories will be investigated for associations to cognitive measures (general intelligence, executive functioning and memory).

13.4 Sample size justification

13.4.1 Trial

The anticipated sample size is approximately 226 participants. This sample size is based on the expected eligible clinic prevalence of gender-related distress, allowing for sufficient power to estimate the posterior distributions of treatment effects and to detect meaningful differences and associations in the primary and secondary outcomes.

Using simulations, it was determined that with 226 participants the trial would have the equivalent of 91% power with a standardised effect size (SES) of 0.525. For the primary outcome, the SES of 0.525 means a difference of 5.25 points on the standardised KIDSCREEN-10 t-score, where the standard deviation is 10 for all t-scores at all timepoints.

If recruitment is lower than expected, the probability of detecting the same SES will be lower. If only 150 participants are recruited, the trial would still have the equivalent of 80% power to detect the SES of 0.525.

As the eligibility criteria for the trial cannot be changed or widened as would be common in a poorly recruiting trial, nor more sites added, other options would have to be considered to reach the target sample size of 226. This could include extending the recruitment period and therefore timeline for the trial. Interim analyses can also be carried out at pre-specified points where decisions on the continuation of the trial can be taken. All amendments to the trial will be approved by both the DMC and the PSC committees before being enacted.

The electronic version of this document is the latest version. It is responsibility of the individual to ensure that any paper material is the current version. Printed material is uncontrolled documentation.

13.4.2 HORIZON INTENSIVE

The sample size for HORIZON INTENSIVE will be 300. These 300 participants will, in general, be matched to participants in the trial based on the stratifying factors of the trial randomisation(substituting chronological age as a proxy for Tanner stage). This will be done by recruiting participants to HORIZON INTENSIVE at intervals, after assessing the general stratification factors of participants randomised into the trial.

With 300 participants, there is sufficient power to test the intensive participants against those participants in the trial immediate arm. We will be able to detect a SES of 0.42 with the equivalent of 90% power (300 vs 112). We will have the equivalent of 90% power to detect a 0.32 SES for intensive participants to be tested against the whole trial population (300 vs 226).

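### In Protocol 13.4.2 the detectable effects of 0.42 and 0.32 do not follow from the group sizes printed beside them (300 v 112 and 300 v 226)

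*Protocol*

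**What the plan says.** Section 13.4.2 fixes the cohort: "The sample size for HORIZON INTENSIVE will be 300". It then makes two power statements.

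- Against the immediate arm: "We will be able to detect a SES of 0.42 with the equivalent of 90% power (300 vs 112".
- Against both arms together, again at 90% power: "detect a 0.32 SES for intensive participants to be tested against the whole trial population (300 vs 226".

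The section gives no alpha, sidedness, attrition rate or method. Section 13.4.1 sets the scale for the effect sizes, "where the standard deviation is 10 for all t-scores at all timepoints", so an effect of 0.42 is 4.2 points. It also reports the trial's own power at an effect of 0.525: "Using simulations, it was determined that with 226 participants the trial would have the equivalent of 91% power". For low recruitment it adds: "If only 150 participants are recruited, the trial would still have the equivalent of 80% power to detect the SES of 0.525". It states no attrition rate either.

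Table 1 (section 1.4) puts 113 participants in each trial arm. That agrees with 226 randomised 1:1 under section 6.1. Section 13.4.2 prints 112.

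**The concern.** Each effect is tied to an explicit pair of sample sizes, so it can be checked, and neither effect matches its pair. This is not detail left to the analysis plan, because the protocol prints the numbers itself.

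These two figures are the only quantitative support for the number 300. Participants in that cohort do not receive GnRHa but undergo blood tests, DEXA scans and cognitive testing. As the text stands, a reader cannot tell whether 0.42 and 0.32 describe full recruitment, the low-recruitment case of 150, or full recruitment with an undeclared allowance for loss. Anyone using them to judge the sensitivity of the non-randomised comparison would be working from figures of unknown origin.

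**Working it through.** **Inputs.** Cohort 300; trial groups 112 and 226; power 90%; SD of 1 on the effect-size scale (13.4.1 and 13.4.2). Alpha is assumed two-sided 5%, by analogy with the 95% credible interval in 13.5.1.1. Attrition is assumed to be zero at first and is then varied.

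**Formula.** Detectable SES = (z for alpha + z for power) × √(1/n₁ + 1/n₂), with 1.960 + 1.2816 = 3.2415.

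**1. The plan's own figures.**

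- 300 v 112: 3.2415 × √(0.003333 + 0.008929) = 3.2415 × 0.11073 = 0.359 (noncentral t 0.360). Printed: 0.42.
- 300 v 113: 0.358 (noncentral t 0.359).
- 300 v 226: 3.2415 × √(0.003333 + 0.004425) = 3.2415 × 0.08808 = 0.286. Printed: 0.32.

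On the T-score scale that is about 3.6 and 2.9 points, against the printed 4.2 and 3.2.

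**2. Power at the printed effects.**

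- 0.42/0.11073 − 1.960 = 1.833, giving 96.7% (noncentral t 96.6%).
- 0.32/0.08808 − 1.960 = 1.673, giving 95.3% (noncentral t 95.2%).

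A one-sided 5% test widens the gap, to 98.4% and 97.7%.

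**3. Can one shared unstated input explain both?** Alpha, power, a common retention rate and a common variance factor all multiply both effects equally. The ratio of the two effects is therefore fixed by the sizes: 0.11073/0.08808 = 1.257. Allowing for rounding, the printed pair needs a ratio between 0.415/0.325 = 1.277 and 0.425/0.315 = 1.349, so no shared input gives both.

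- Common retention: 0.42 needs 71.3% to 74.8%, while 0.32 needs 77.2% to 82.2%. The ranges do not overlap.
- Common alpha: 0.42 needs about 0.012 and 0.32 about 0.019. At 0.0125 the pair is 0.42 and 0.33; at 0.0167 it is 0.41 and 0.32.

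**4. What does return both values?**

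- 300 v 75: 3.2415 × √(0.003333 + 0.013333) = 0.4185, printing as 0.42. Power at 0.42 is 90.2%.
- 300 v 150: 3.2415 × √(0.003333 + 0.006667) = 0.3242, printing as 0.32. Power at 0.32 is 89.3%.
- Unequal loss from the printed sizes also works. With 32% lost in the trial and none in the cohort (300 v 76.2 and 300 v 153.7), the effects are 0.416 and 0.322. With 30% and 10% (270 v 78.4 and 270 v 158.2), they are 0.416 and 0.3246. More generally, about 32% to 34% loss in the trial with none in the cohort, 31% to 32% with 5%, or 30% with 10% reproduces both.

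**5. Cross-check on 13.4.1.** The same formula at an effect of 0.525 gives 97.6% for 113 per arm (stated 91%) and 89.5% for 75 per arm (stated 80%; noncentral t gives 89.1%). The trial's own powers therefore also fall below the plain no-loss formula.

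**The case against.** The strongest reply is that the benchmark may not be the method used. Section 13.4.1 says that its powers came from simulation, and both sections speak of equivalent power. The no-loss formula misses the trial figures in the same direction, so an undisclosed allowance across the whole of 13.4 is a live explanation. A common loss of 25% brings all four stated powers within two points: 90.7% and 88.2% (stated 90%), 92.8% (stated 91%) and 79.5% (stated 80%). Two-decimal agreement may be too much to ask of simulated results.

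Part of this stands. It rules out calling the figures simply erroneous, and it means that zero loss is an assumption too. It does not rescue the text. At 25% common loss the detectable effects are 0.4145 and 0.3297, which print as 0.41 and 0.33. Under any loss explanation, the sizes in brackets are not the sizes analysed.

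A reader might infer from the 75 and 150 match that the figures can only have come from the low-recruitment case. The documents do not show this. Section 13.4.2 mentions no fallback, and unequal loss fits equally well. A 30% trial loss even returns the 91% stated for 226, although it gives 76.7% for 150 where 80% is stated.

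A reader might also infer that the cohort is the wrong size. The arithmetic does not support that: without loss the printed effects understate what 300 can detect, so the claim of sufficient power holds.

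**Conclusion.** The point holds as a reporting error of minor severity. The printed effects exceed those that belong to the printed sizes by about 17% (0.42 against 0.36) and 12% (0.32 against 0.286), or equivalently power is about 97% and 95% where 90% is stated. The sizes of these gaps rest on two-sided 5% and no loss, neither of which the protocol states. The finding that no common adjustment gives both figures does not depend on those choices, though it does assume that effects from a closed formula are comparable with the planners' figures to two decimals. Where the figures came from is not established. The difference between 112 and 113 needs no statistical assumption.

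**What to change.** Go back to the original calculation or simulation and confirm which analysed sizes, alpha, sidedness and attrition produced 0.42 and 0.32. Then print effects and sizes that belong together:

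- if no loss is assumed, 0.36 for 300 v 113 and 0.29 for 300 v 226;
- otherwise, keep 0.42 and 0.32 with the sizes actually analysed, and say whether they reflect attrition or a smaller trial.

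The provenance has to be confirmed first. Relabelling the figures as the 150-participant case, or printing no-loss effects, without that check could replace one unsupported statement with another. State the attrition assumption once and use the same one in 13.4.1 and 13.4.2. Correct 112 to 113 to agree with Table 1.

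The cost is a few lines of protocol text. Recruitment, assessments and analysis are unaffected.

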13.4.3 CONNECT

The planned sample size for PATHWAYS CONNECT is 250 participants; 150 from TRIAL (75 per arm), 100 from HORIZON INTENSIVE. We are assuming a small-to-medium effect size (partial eta²=0.03) and a conservative rate of dependent variable autocorrelation within subject (0.5, other studies in adolescents and late childhood have shown values >0.7). With a sample size (minimum) per group of 49 across all 3 time points, the study is well powered ($\alpha<0.001$, $\beta>0.9$) to detect interactions between treatment group and volumetry over the 3 timepoints while also allowing for multiple testing / comparison correction (calculated using G*Power).

We will also use a normative modelling approach to understand individual differences in brain development in CYP⁴⁷. In the absence of prior data in the same age range and characteristics, we estimate effect size by comparing $n = 89$ children with born prematurely to a term-born volumetric growth curve of healthy children derived from $n = 275$ using Gaussian process regression. This found a large effect size versus 0 (preterm mean $Z = 1.78$ and SD of $Z = 1.94$, cliff's delta = 0.62). Assuming a medium effect size of GnRHa treatment on brain tissue volumes (Cohen $d = 0.5$) and with alpha = 0.05 and beta (power) = 0.9, we would need a sample size of $n=36$. Assuming a more realistic small effect size (Cohen $d = 0.3$) and with alpha = 0.05 and beta (power) = 0.9, we would need a sample size of $n=97$.

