4.17 Magnetic Resonance Imaging Data

Participants consenting to take part in PATHWAYS CONNECT will undergo structural and functional MRI imaging (sMRI/fMRI) at baseline, month 12 and month 24 as per the Schedule of Events. HORIZON INTENSIVE participants will be scanned at baseline and 24 months only. The final scanning window will be 6 weeks before/after the final treatment administration.

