13.5.3 Statistical methods for exploratory analyses

13.5.3.1 CONNECT

To explore individual differences, a normative modelling framework has been developed by CONNECT researchers for use in multimodal neonatal brain imaging data, that is both sensitive to brain growth and the diffuse brain changes seen following prematurity and in individuals with autism across childhood and adulthood. This approach provides an individual index of variation from the typical distribution from as early as birth, corrected for age or sex, per modality and region, capturing inter-person heterogeneity. This measure of variation has also proven a useful intermediate phenotype to interrogate pathways out to cognitive function in early life. An important advantage of our approach is that we can develop growth curves across different MRI modalities. We will use 'normative modelling' (Gaussian Process Regression or similar Bayesian approach) to assess brain maturation of patients in each study arm with reference to adolescent brain structural, functional and metabolite reference values built from existing studies. An individual Z-score then captures deviations from age-expected reference and can be used to examine either correlations with outcome measures or individual differences in brain changes with respect to GnRHs.

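### CONNECT's minimum of 49 per group assumes three scans in every group, which HORIZON INTENSIVE does not have, and its 36 and 97 are undeclared one-sided figures; the planned 250 still holds up for the interaction

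*Protocol*

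**What the plan says.** Section 13.4.3 plans 250 participants: "150 from TRIAL (75 per arm), 100 from HORIZON INTENSIVE". It gives two sample-size arguments.

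- **Group-by-time interaction.** The inputs are partial eta-squared 0.03 and a within-subject correlation of 0.5, which the text calls conservative. It concludes: "With a sample size (minimum) per group of 49 across all 3 time points, the study is well powered", with alpha below 0.001 and power above 0.9. The effect tested is the interaction of treatment group with volume over three time points.
- **Normative model.** With alpha 0.05 and power 0.9, d = 0.5 is said to need n = 36. The text then continues "Assuming a more realistic small effect size", d = 0.3, which is said to need n = 97. It does not state whether the test is one- or two-sided, or whether n is per arm.

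On the scans, section 4.17 says: "HORIZON INTENSIVE participants will be scanned at baseline and 24 months only". Section 1.3.2 and Table 6 in Appendix A agree. The CONNECT synopsis names three groups for comparison: immediate start, delayed start and HORIZON INTENSIVE. Section 13.5.1.3 specifies linear mixed models with subject as the random effect. Section 13.5.3.1 says the normative model will "assess brain maturation of patients in each study arm with reference to adolescent brain structural, functional and metabolite reference values".

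**The concern.** The interaction calculation requires three scans from every group it counts. HORIZON INTENSIVE, the only comparison group without GnRHa through month 24, has two. The stated minimum is therefore computed for a design the protocol does not run. Anyone monitoring recruitment or scan loss against 49 per group would think the study had more slack than it has.

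The normative figures raise a separate problem. The aims in the CONNECT synopsis and section 2 are whether GnRHa affects brain development or alters its trajectory, with no direction given, so a two-sided test is the natural reading. The 97 quoted for the effect the protocol regards as more realistic also exceeds the 75 in each TRIAL arm, and section 13.5.3.1 reads as a per-arm analysis. Finally, section 13.4.3 describes d as an effect of GnRHa treatment, whereas a one-sample test measures only how far a group lies from an external reference.

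**Working it through.** **Inputs (section 13.4.3).** Partial eta-squared 0.03, so f² = 0.03/0.97 = 0.0309 and f = 0.176; correlation 0.5; alpha 0.001; groups of 75, 75 and 100. Scans: three in each TRIAL arm, two in HORIZON INTENSIVE (section 4.17).

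**Interaction formula.** Repeated-measures ANOVA, within-between interaction, using G*Power's default effect-size definition and sphericity. With N participants, k groups and m scans, the non-centrality is λ = f²·N·m/(1 − 0.5), with df1 = (k − 1)(m − 1) and df2 = (N − k)(m − 1).

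**Reproducing the stated figure.** Three groups, three scans, 49 per group (N = 147):

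- f rounded to 0.18: λ = 0.0324 × 147 × 3/0.5 = 28.6, df 4 and 288, power 90.0%.
- f unrounded: λ = 27.3, power 88%. The gap is rounding of f and is not held against the plan.

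At the stated alpha, 49 fits three groups with three scans each and neither of the designs below.

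**The designs the scan schedule allows** (alpha 0.001, f unrounded):

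| Design | N | λ | df | Power |
|---|---|---|---|---|
| 3 groups × 2 scans, 49 per group | 147 | 18.2 | 2, 144 | 72% |
| 3 groups × 2 scans, smallest N for 90% | 200 (about 67 per group) | 24.7 | 2, 197 | 90% |
| 3 groups × 2 scans, planned total | 250 | 30.9 | 2, 247 | 97% |
| 2 TRIAL arms × 3 scans, 49 per arm | 98 | 18.2 | 2, 192 | 73% |
| 2 TRIAL arms × 3 scans, smallest N for 90% | 132 (66 per arm) | 24.5 | 2, 260 | 90% |
| 2 TRIAL arms × 3 scans, planned | 150 | 27.8 | 2, 296 | 95% |

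The row for 250 treats the groups as equal in size, an approximation to 75/75/100.

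**Attrition margin per TRIAL arm.** Against 49: (75 − 49)/75 = 35%. Against 67: (75 − 67)/75 = 11%. Against 66: 12%.

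**Normative model.** Exact one-sample t-test, non-centrality d·√n, alpha 0.05:

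| d | n for 90%, one-sided | n for 90%, two-sided |
|---|---|---|
| 0.5 | 36 (power 90.3%) | 44 |
| 0.3 | 97 (power 90.1%) | 119 |

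The protocol's 36 and 97 are the one-sided column exactly. A two-sample test does not give them: one-sided it needs 70 and 191 per group, two-sided 86 and 235.

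Power at d = 0.3 for the sizes available:

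- One TRIAL arm, n = 75: 82% one-sided, 73% two-sided. The effect detectable with 90% power two-sided is about d = 0.38.
- Both TRIAL arms pooled, n = 150: about 95% two-sided.

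**The case against.** The strongest reply is that the conclusion survives. The protocol calls 49 a minimum, plans 75/75/100, and at that size both feasible interaction tests exceed 90% at a strict alpha. This stands. A reader might infer from the 72% that CONNECT is underpowered for its main comparison; the documents do not support that, because nobody plans to stop at 147.

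Three further points carry weight.

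- The planned analysis is a mixed model, which accepts two scans from one group and three from the others. The three-by-two calculation discards the TRIAL month-12 scans, so 67 per group is conservative. The 66 per arm for TRIAL alone uses all three scans and is not affected.
- The protocol cites correlations above 0.7. At 0.7, 147 participants with two scans would have 96% power. But 0.5 is the value the protocol chose to plan on, and its minimum should follow from that value.
- At alpha 0.01, 49 per group does result from either feasible design (N = 97 for two arms with three scans; N = 146 for three groups with two scans). The alpha may therefore be what is misreported. Section 13.4.3 states 0.001 and three time points, so the text needs correcting either way.

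On the normative model, a reader might infer that the study misses its own requirement of 97. That goes too far. Section 13.4.3 does not say 97 is per arm, the model's output is an individual Z-score, and pooled TRIAL (150) exceeds both 97 and 119. The per-arm shortfall follows only if section 13.5.3.1 is read as a separate test in each arm. A one-sample test of Z against zero is also coherent for a normative model, and the comparison by study arm is provided for in section 13.5.1.3. What remains is that sidedness and unit are unstated and that d is labelled as a GnRHa effect.

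Section 13.3 declares CONNECT's outcomes exploratory with no primary outcome, which limits the consequence. No section plans to conclude safety from a null imaging result.

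**Conclusion.** The sample-size text is wrong as written; the planned sample size is not shown to be inadequate. At the stated alpha, effect size and correlation, the minimum is about 66 to 67 per group instead of 49, and 49 would give about 72 to 73%. The tolerable loss per TRIAL arm is about 11 to 12%, where the text implies 35%. At 75/75/100, power for the interaction is about 95 to 97%.

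The normative figures are one-sided without saying so; two-sided they are 44 and 119. Whether d = 0.3 is covered depends on a choice the protocol leaves open: 73% two-sided per arm, about 95% with the TRIAL arms pooled.

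The interaction figures assume sphericity and G*Power's default effect-size definition. The protocol does not name the definition, but the default reproduces its 49; the SPSS-type option would give only about 17% for the same three-by-three case.

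**What to change.** In section 13.4.3:

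1. Replace the statement of 49 per group over three time points with power and minimum n for the actual schedule: 75 v 75 over three scans (95%, minimum 66 per arm), and 75/75/100 at baseline and month 24 (about 97%, minimum about 67 per group). Note that the latter is conservative because the mixed model also uses the TRIAL month-12 scans. If alpha 0.01 was intended, say so and give the figures on that basis.
2. Replace 36 and 97 with the two-sided 44 and 119.
3. State whether the normative n is per arm or pooled, and give the power at 75 per arm for d = 0.3 (73% two-sided, with about d = 0.38 detectable at 90%).
4. State that the one-sample figure concerns deviation from the reference population and is not the power for a between-arm effect of GnRHa.

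The cost is restated, less favourable figures. No extra participants, scans or changes to the analysis are needed.
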